Pilot of a Linguistically Adapted CBSM Intervention with Limited Attention to Culture. We conducted a linguistic translation of CBSM for PC survivors treated for localized disease who were Spanish monolingual men. Based on this preliminary work and literature describing shared cultural processes that may interact with chronic disease management, 75,34 we translated the intervention using a professional company and internal verification and conducted some minor adaptations of the C- CBSM intervention to address how factors such as allocentrism and fatalism impact distress, interpersonal relations, self-management and health behaviors. We then conducted 12 focus group sessions following an iterative approach where we first presented the adapted C-CBSM to interventionists (n=4) and health care providers (n=8; Sessions 1-4) and incorporated revisions, then presented the revised CBSM to ten Hispanic PC survivors (Sessions 5-8) and added further revisions based on their feedback. Finally, we presented the further revised CBSM to interventionists, providers and patients combined (Sessions 9-12) and subsequently derived the final version. The vast majority (85-90%) of interventionists, providers and patients rated the final revision of C-CBSM "highly acceptable" and "highly relevant" to the needs of Hispanic PC survivors. Based on this qualitative work, we conducted a pilot study (N=71; surgery n=32; radiation n=39; all localized PC), ⁹⁸ of this version of CBSM developed following standard adaptation procedures (e.g., information gathering, focus groups, expert & patient review). 75,44 Acceptance rate for fully eligible participants was 42% and attendance was 80%. Assignment to C-CBSM, relative to controls (one-day seminar), showed significant improvements in FACT total, physical and emotional well-being, and EPIC sexual functioning, provided

preliminary data on the feasibility and acceptability (80% attendance), as well as some preliminary efficacy on improving symptom burden and HRQoL for Hispanic PC survivors.

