To Test Exploratory Hypotheses. Aim 3: For Hypotheses 3, the linear mixed model will include fixed effects for the experimental group (C-CBSM vs. CBSM) and observation time (T1-T4), and random effect for person with a compound symmetry covariance structure for the repeated residuals within person. A group by time interaction and post-hoc tests on this model effect will indicate whether and how the time course of the dependent variable differs between the groups. Hypotheses 1-3 will all be analyzed in a similar manner using the outcome measures described in sections C.6.c (Primary Outcomes), C.6.d (Intervention Targets) and C.6.e (Inflammation) respectively. These measures include markers of symptom burden, systemic inflammation, and cytokine production following cellular activation with TLR ligands. Data from gene expression profiling are analyzed using advanced bioinformatics techniques, and described in C.6.e, and as reported previously by Antoni et al.¹²⁴ As each outcome across the different study hypotheses have been carefully selected to address a priori hypotheses, no adjustment for testing of multiple outcomes will be made. However, within the analysis of a specific outcome, Tukey or Bonferroni adjustment will be made for the multiple tests across different time points. The power calculation below adjusts for this multiplicity. Aims 4a-4c: These hypotheses involve tests of proposed mediators of C-CBSM's effect on our primary outcomes. To test mediation with LGM, individual change trajectory (in each outcome of interest) is characterized by an intercept and a slope factor. The overall pattern of change (e.g., linear, quadratic, etc., as informed by analyses for Aims 1-3) for the whole group can be specified by a particular set of coefficients associated with the slope factor. First, we will specify a growth curve model for all participants with an intercept factor representing our outcome of interest at baseline, and the slope factor reflecting the change trajectory in our outcome measure from T1 to T4. For example, to test that increased stress management skills (e.g., MOCS) in the C-CBSM group accounts for reductions in symptom burden (e.g., EPIC-S), we will first test a LGM model without the stress management skills (the mediator) and then test the model with change in stress management skills from T1 to T4. In the model without the stress management skills, we expect that group assignment is not related to baseline symptom burden, but that group assignment will be related to a greater negative change (reduction) in symptom burden scores. In the next step, we will add stress management skills and expect that after adding this mediator in the model, the path between group assignment and symptom burden slope will become non-significant, while the path between the mediator and symptom burden slope is significant thus suggesting mediation. This approach will be applied to test all mediation models in hypotheses 4a-4c. 191,192 Aim 5a-5b: To evaluate moderators and mechanistic pathways of C-CBSM's effects, we will use LMM and latent variable mediation models. For Hypothesis 5a, we will test moderation by including interaction terms between group assignment (C-CBSM vs. CBSM) and each moderator of interest (e.g., SES, acculturation, Hispanic ancestry, treatment type) within the LMM framework. These models will include fixed effects for group, time (T1-T4), the moderator, and the group × moderator and group × time × moderator interactions. A significant three-way interaction (group × time × moderator) will indicate that change in the outcome (e.g., inflammation, symptom burden, HRQoL) over time differs by both treatment group and the level of the moderator. Post-hoc comparisons will clarify the nature of the moderation effects across timepoints. For Hypothesis 5b, we will test whether improvements in cardiometabolic markers (e.g., lipids, fasting glucose, blood pressure) in the C-CBSM group are mediated by reductions in inflammation using SEM. Parallel process LGMs will estimate trajectories for inflammatory markers and cardiometabolic outcomes across time. The indirect effect from group assignment to cardiometabolic outcome slope via inflammation slope will be tested. This approach allows for simultaneous modeling of changes over time, capturing both within- and between-subject effects. Model fit will be evaluated using standard criteria (CFI > .95, RMSEA ≤ .05, SRMR < .08), and significance of indirect effects will be tested using bias-corrected bootstrapped confidence intervals.

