
Preliminary Analyses and other Statistical Considerations. Descriptive statistics will be computed to ensure values are within expected ranges and to eliminate any errors. We will use PRELIS2^{193,194} to examine multivariate normality. Non-normally distributed variables will be transformed using log transformations. We will compute estimates of internal consistency (Chronbach's α) for all scales and composite scores. If reliability is <.70, we will evaluate the internal consistency of the measure and delete items or subscales as needed.¹⁹⁵

Power Analyses. The primary aim compares pre-post change in symptom burden scores between the randomized arms. A sample of 100 per arm is assumed, although T1-T3 time points will have larger samples. Power is based on the effect size defined as the group difference in the mean change divided by the standard deviation of the change. Power calculations are based on effects of the C-CBSM pilot study. With 100 per arm, there is 80% power to detect an effect size of 0.40 assuming a two-tailed test and a Type I error rate of 5%. Since multiple tests look at change in various post-intervention time points, using a Type I error rate of 1% results in a detectable effect size of 0.49. If effect sizes are calculated from Figure 6 from our preliminary work, then the observed effect sizes as defined above are 0.52 for FACT-G and 0.40 for EPIC-S. Effect sizes for subscales FACT-PWB and FACT-EWB are

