0.81 and 0.42 respectively. With greater effect sizes anticipated in the proposed study, the sample size of at least 100 per arm has sufficient power to detect differences even after adjusting for the analysis of change from baseline to post-intervention time points. Power for C-CBSM's effect on down regulation of inflammatory genes are based on Antoni et al.¹²⁴ study which indicated that the observed effect size was one standard deviation in a sample size of 45 in the experimental condition. Glucocorticoid receptor sensitivity demonstrated similar effects. With a T4 sample size of 100 in the C-CBSM group, effect sizes of 0.48 standard deviations are detectable with 80% power at a 2-tailed Type I error rate of 1%, so that expected effects will be detectable with sufficient power. While pilot data are not available for all outcome measures, the constant in the power calculation regardless of the outcome is the effect size expressed in terms of standard deviations, which is 0.40 or 0.49 depending on whether the Type I error rate is 5% or 1%.

Covariates, Cohort Effects, Intent to Treat & Missing Data. A number of variables (e.g., SES, disease factors) will be considered as possible covariates. These putative confounds will be entered as covariates if correlated with our outcomes (at p<.10). Random assignment should render groups equivalent on covariates and this will be verified post-hoc. We will test differences among cohorts who have completed our conditions by doing an ANOVA within each condition with k levels of cohort. If we find a cohort with differential outcomes (significant Condition x Cohort x Time interaction), we will conduct a Group x Time interaction tested within each cohort, and a Cohort x Time interaction tested within assignment. We have never observed a significant cohort effect in prior CBSM work. We will also use an intent-to-treat approach in that all participants will be retained in the analysis, including those with missing data at time points by using full information maximum likelihood (FIML) estimation. FIML, a recommended state-of-the-art method, 197,198 uses all available data for each participant and provides unbiased estimates of parameters when the data are missing at random.

Cost to the Participants:

There will be no cost to the participants for taking part in this study. All expenses related to the study activities, including laboratory tests done and lab materials.

Risk and Benefits:

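### Sufficient power after adjustment is claimed without an effect size for C-CBSM versus 10-week CBSM, and assumes 100 per arm at T4 where the protocol's own retention figures give 70 to 78

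*Combined protocol and SAP*

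**What the plan says.** The Power Analyses paragraph starts from this: "A sample of 100 per arm is assumed, although T1-T3 time points will have larger samples". Effects are between-arm differences in mean change, in units of the SD of change. The paragraph gives 80% power for 0.40 at a two-sided 5% level. To allow for several follow-up times, it adds that "using a Type I error rate of 1% results in a detectable effect size of 0.49".

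On the source of the effects it says: "Power calculations are based on effects of the C-CBSM pilot study". It then reports, from a Figure 6 of preliminary work, that "the observed effect sizes as defined above are 0.52 for FACT-G and 0.40 for EPIC-S", with 0.81 for FACT-PWB and 0.42 for FACT-EWB. The conclusion is: "With greater effect sizes anticipated in the proposed study, the sample size of at least 100 per arm has sufficient power to detect differences", and the sentence goes on to extend this to the adjusted analysis.

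Other sections bear on that conclusion:

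- To Test Exploratory Hypotheses says that within each outcome "Tukey or Bonferroni adjustment will be made for the multiple tests across different time points", and adds: "The power calculation below adjusts for this multiplicity".
- The pilot section gives the pilot's comparator: "Assignment to C-CBSM, relative to controls (one-day seminar), showed significant improvements in FACT total, physical and emotional well-being, and EPIC sexual functioning".
- Randomization Protocol describes this trial's control as translated CBSM in ten weekly 90-minute sessions, with the same CBT components but no cultural adaptation.
- Participants gives about 200 men. Randomization Protocol projects 140 at T4. Experimental Design estimates attrition of about 22%.

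**The concern.** The conclusion depends on effects being larger than those already seen, and nothing in the documents gives that a size. The comparator also moves the other way. The pilot compared an intervention with a one-day seminar. This trial compares two 10-week programmes that share their active content, and the Benefits section expects both to help. An effect over a seminar does not estimate an increment over CBSM. The protocol's own discussion of innovation criticises earlier trials because inert or inadequate comparators could not show the increment.

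The T4 sample size is a second difficulty. If follow-ups before T4 are to have more than 100 per arm, then 100 is the T4 number. With about 200 enrolled in all, 100 per arm is roughly everyone randomised, which leaves no room for the losses planned elsewhere.

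A reader who takes the sentence at face value could read a null EPIC-S result as good evidence that cultural adaptation adds nothing. The plan does not establish the power needed for that.

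**Working it through.** **Inputs.** From Power Analyses: n = 100 per arm, two-sided 5% and 1%, 80% power, and effects of 0.40 (EPIC-S), 0.42 (FACT-EWB), 0.52 (FACT-G) and 0.81 (FACT-PWB). From the sections named above: about 200 enrolled, 140 retained at T4, about 22% attrition. Hypothesis 1 has three follow-ups, so a Bonferroni level of 0.05/3 is shown beside the plan's 1%. Observations are treated as independent, as the plan does.

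**Reproducing the plan.** Detectable effect = (z for α/2 + z for power) × √(2/n).

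- 5%: (1.960 + 0.842) × √(2/100) = 0.396; noncentral t gives 0.398.
- 1%: (2.576 + 0.842) × √(2/100) = 0.483; noncentral t gives 0.487.

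The plan's 0.40 and 0.49 are confirmed. At 0.05/3 the noncentral t gives 0.461.

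**Power at the quoted effects, 100 per arm** (noncentral t):

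| Outcome | Effect | 5% | 0.05/3 | 1% |
|---|---|---|---|---|
| EPIC-S | 0.40 | 80% | 66% | 59% |
| FACT-EWB | 0.42 | 84% | 71% | 64% |
| FACT-G | 0.52 | 96% | 90% | 86% |
| FACT-PWB | 0.81 | >99% | >99% | >99% |

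For EPIC-S to reach 80% power after adjustment, the increment over 10-week CBSM would have to be 0.461/0.40 = 1.15 times (0.05/3) or 0.487/0.40 = 1.22 times (1%) the quoted effect.

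**Source of the effects.** Power Analyses names the pilot. The pilot's four significant outcomes (FACT total, physical, emotional, EPIC sexual) correspond to the four effects quoted. One label differs: FACT total in the pilot section, FACT-G in the power section. The earlier CBSM trial also used a one-day seminar as control, so the comparator differs from this trial's whichever of the two studies Figure 6 shows.

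**T4 numbers.** 140/2 = 70 per arm. 200 × (1 − 0.22)/2 = 78 per arm. The two retention statements also disagree: 140 of 200 is a 30% loss, not 22%.

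| Per arm at T4 | Detectable, 5% | Detectable, 1% |
|---|---|---|
| 100 (plan) | 0.398 | 0.487 |
| 78 | 0.4514 | 0.5532 |
| 70 | 0.4769 | 0.5847 |

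On completers at T4, FACT-G at 0.52 also falls below the 1% detectable effect, with power of about 74% (78 per arm) or 68% (70 per arm).

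**The case against.** The strongest reply is that the sentence is conditional. It claims sufficiency for effects larger than the pilot's, so showing that pilot values miss 0.49 does not contradict it. That stands: the sentence is unsupported, not refuted. A reader might also infer an error in the power arithmetic, but 0.40 and 0.49 both reproduce.

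The plan does offer qualitative reasons to expect more. The intervention was modified after the pilot, the pilot itself gave limited attention to culture, and culturally adapted CBT for depression is said to outperform standard treatment. These are fair reasons for optimism, but none gives a size and none deals with the stronger comparator.

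The link between Figure 6 and the pilot is an inference, although a strong one. The authors should confirm it before the text states it as fact.

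Power Analyses ends by acknowledging that pilot data are missing for some outcomes and that the detectable effect is 0.40 or 0.49 whatever the outcome. That is a sound statement for 100 per arm, but it does not rescue the conclusion about sufficiency.

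Finally, the planned likelihood analysis uses all available data, so men who miss T4 still contribute. The completer figures are therefore approximations and on that account tend to be cautious.

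**Conclusion.** The point holds as a lack of support combined with an inconsistent T4 sample size. No document figure supports a larger effect for C-CBSM over 10-week CBSM. At the quoted effects with 100 per arm, adjusted power is 59% to 66% for EPIC-S, the only symptom-burden effect given, and 64% to 71% for FACT-EWB. At T4 the protocol's own retention figures imply 70 to 78 per arm. The detectable effect there is about 0.45 to 0.48 at 5% and 0.55 to 0.58 at 1%, against the stated 0.40 and 0.49.

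Two stronger readings are not supported. One is that the trial is underpowered and must enrol more men. The true increment is unknown, so the documents show neither adequate nor inadequate power. The other is that every primary outcome falls short. With 100 per arm, FACT-G and FACT-PWB clear 0.49 at face value, although apparently as effects over a seminar.

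These results rest on the plan's change-score simplification, independent observations, equal arms, and completers only at T4.

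**What to change.** Change the wording of Power Analyses only:

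1. Delete the opening clause about larger anticipated effects and the general conclusion that power is sufficient.
2. Reconcile the 140 retained with the 22% attrition, and restate the T4 detectable effect for the number expected. On completers it is about 0.45 (5%) and 0.55 (1%) with 78 per arm, or 0.48 and 0.58 with 70 per arm. Note that these approximate the planned likelihood analysis. Keep 0.40 and 0.49 only for time points where 100 per arm are expected.
3. Once the authors have confirmed that Figure 6 shows the pilot, add text such as:

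> The preliminary effects were measured against a one-day seminar. They do not estimate the increment of C-CBSM over 10-week CBSM, for which this protocol has no estimate. At those values, power after adjustment for time points is below 80% for EPIC-S and FACT-EWB.

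The cost is a few sentences and a less favourable power statement. Enrolment, endpoints, model and significance levels stay as they are.

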CBSM & Physiological Adaptation. We documented CBSM's effects on diurnal cortisol, circulating inflammatory markers and pro-inflammatory gene expression in circulating leukocytes. 124 In 84 PC survivors about 10.3 months post surgical or radiation treatment undergoing hormonal therapy, pro- inflammatory cytokines were associated greater symptom burden. Better urinary function pre- to post- CBSM was associated with decreases in both IL-1 (r=-.55) and IL-6 (r=-.40). Similarly, decreases in fatigue across the intervention period were associated with decreases in IL-1 \square (r=.41) and IL-6 (r=.35). We also found that decreases in IL-6 were associated with increases in both physical (r=-.38) and social (r=-.37) functioning, and decreases in anxiety (r=.40), while decreases in IL-1 were associated with decreases in both CES-D depression (r=.40) and an ABS negative mood composite (r=.41; all p's <.05). In stage 0-III breast cancer (BC) survivors, CBSM reduced cortisol, changed circulating numbers of specific leukocyte subsets and cytokine production by T lymphocytes. 121,123,124,125 CBSM-treated BC survivors also showed reductions in expression of leukocyte pro-inflammatory gene pathways and enhanced expression of innate antiviral gene pathways. Genome-wide transcriptional profiling and bioinformatics analyses were conducted at baseline and 6- and 12-months post-CBSM in 79 BC survivors randomized to CBSM or health promotion. At baseline, negative affect was associated with a >50% differential expression of 201 leukocyte transcripts. This included upregulated expression of pro-inflammatory and metastasisrelated genes. CBSM altered leukocyte expression of 91 genes by >50% at follow-up. Effects included downregulation of pro-inflammatory (e.g., IL-1A, IL6, TNFA) and metastasis-related (MMP9) genes and upregulation of Type I interferon (IFN) response genes. Promoter-based bioinformatic analyses showed a decreased activity of NF-kappaB/Rel and GATA family transcription factors and increased activity of IFN response factors and the glucocorticoid receptor, suggesting these as mediators of CBSM-induced reversal of upregulated inflammatory gene expression. 124 Although highly efficacious, active treatment (e.g., surgery & radiation; $\sim 70\%$ of cases) for localized prostate cancer (PC) can lead to significant symptom burden (i.e., sexual & urinary dysfunction) and compromises in multiple facets of health related quality of life (HRQoL). Hispanic PC survivors are at a physical and psychosocial disadvantage, yet evidence based treatments (EBTs) such as cognitive behavioral stress management (CBSM) that have proven effective in reducing symptom burden and improving HRQoL in cancer survivors have rarely targeted Hispanics or delivered culturally adapted CBSM in Spanish to diverse Hispanics in the context of a randomized behavioral clinical trial with an adequate sample size and long-term followup. This study will fill several critical gaps in our knowledge on the incremental efficacy of culturally adapted EBTs, relative to standard linguistic translations, on improving symptom burden and HRQoL in Hispanic men with localized PC, and map sociocultural, psychosocial and molecular mechanisms involved in the efficacy of CBSM, and therefore help guide targeted treatments for this critically understudied population and other Spanish speaking cancer survivors.

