We conduct genome-wide transcriptional profiling of monocytes, the cells that initiate and maintain most inflammatory responses. 160,161 For in-person blood collection 10-ml of blood are drawn into BD Cell-Separator Tubes. After PBMCs have been isolated through centrifugation, they are labeled with immunomagnetic beads against CD14, ¹⁶² a surface marker specific to monocytes. By passing the labeled cell suspensions through Mitenyi's autoMACS instrument, we can acquire a relatively pure (~90%) population of monocytes through positive selection. The acquired cells will then be lysed and stabilized (RNeasy Mini-Kits), 163 and frozen at -80°C until shipment to UCLA for transcriptome profiling assay. Again, both [name] and [name]'s lab have successfully implemented this protocol in previous collaborations with [name]. 157 [name] lab at UCLA will extract total RNA using PCR-clean and RNAse-free techniques, and check sample quantity and quality with NanoDrop 1000 and Agilent Bioanalyzer 2100 instruments. 150ng of the RNA will be transformed to fluorescent cRNA, hybridized to Illumina Human HT-12 bead arrays, and scanned on a Illumina iScan reader. Raw expression values will be quantile-normalized and log-2 transformed for statistical analysis, and the pool of differentially expressed genes will be identified by Linear Mixed Models that compare CBSM and C-CBSM groups, net of demographic and biobehavioral confounders (e.g. age, BMI, co-morbidities and disease-relevant confounders such as time of treatment, time since treatment). Differentially expressed genes are defined as those showing ≥1.5-fold difference between groups and a transcript-level false discovery rate of < 5% (using standard Benjamini & Hochberg stepdown analysis. 164 Up to 10 differentially expressed genes will be re-verified using quantitative RT-PCR with TaqMan gene expression assays (Applied Biosystems Inc.), a one-step enzyme system, 165 and manufacturer's specified thermal cycling protocol on a iCycler real-time PCR instrument (BioRad Inc.). To identify transcription control pathways underlying differential gene expression, we use a 2-sample variant of the Transcription Element Listening System (TELiS). 166 TELiS quantifies the prevalence of transcription factor-binding motifs within promoters of differentially expressed genes. Analyses focus on 3 transcription factors (TFs) by which C-CBSM could affect monocyte inflammatory activity: NF□B, the major pro- inflammatory TF; CREB, a TF that conveys adrenergic signals to monocytes, and whose activity reflects the amount of SNS signal reaching these cells' genome; and glucocorticoid receptor, a TF that propagates cortisol's anti-inflammatory signals within monocytes and, like CREB, indexes how much hormone signal these cells are registering. For the remote blood collection that is collected via dried blood samples (DBS) we will use standard DBS collection procedures that have been well validated and used by our research team (i.e., [name]). 200, 201 Briefly, the samples are collected by pricking the tip of the middle digit with a sterile disposable lancet, and then allowing drops of blood to wick onto filter paper cards Total RNA will be extracted from DBS samples by cutting 2-4 blood spots from the 5-spot filter paper for each sample (using a separate razor blade for each sample to prevent contamination), depositing all filter paper spots from each sample into 370 µL of RLT in an RNAse-free sterile 1.5 ml microcentrifuge tube, incubating the tube for 30 min at 37° C with agitation (1000 rpm), transferring tube contents (including filter paper) into a QIAshredder column for 60 sec microcentrifugation at maximum speed, after which the 360 µL of remaining RLT was processed through the QIAcube nucleic acid extraction system using RNeasy Micro Kit reagents, the manufacturer's standard operating protocol (including DNAse treatment), and a 20 µL elution volume. DBS samples are highly stable, can sit overnight at room temperature and can be mailed for subsequent storage in a -80 freezer. Samples will be stored/batched at [name] lab and mailed to Co-I [name]'s lab at Northwestern

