Participants will be randomized by cluster randomization (C-CBSM or CBSM) to balance treatment type across conditions. We project to retain 140 participants at our 12-months post-intervention assessment visit (T4). All participants will be asked to participate in 10-weekly 90-minute in person sessions targeting CBT based skills for managing stress and self-management in one of two experimental conditions—a linguistically translated (Spanish) and culturally adapted cognitive behavioral stress and self-management (CBSM) condition (i.e., C-CBSM) or in a standard version of CBSM that is only linguistically translated (CBSM). Following the baseline visit (T1, pre C-CBSM or CBSM), participants are randomly assigned into one of our experimental or control condition groups.

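### The gene-expression power statement assumes no attrition by T4 and borrows its expected effect from a different comparison, so sufficient power is not shown

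*Combined protocol and SAP*

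**What the plan says.** The power statement for gene expression is in the Power Analyses section. It takes its expected effect from an earlier CBSM gene-expression study (reference 124), in which "the observed effect size was one standard deviation in a sample size of 45 in the experimental condition". It then states: "With a T4 sample size of 100 in the C-CBSM group, effect sizes of 0.48 standard deviations are detectable with 80% power". The test level given is two-sided 1%, and the section concludes from this that power is adequate for the effects it anticipates.

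Other parts of the protocol bear on that statement:

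- **Sample at T4.** Participants gives an enrolment of about 200. Randomization Protocol says "We project to retain 140 participants at our 12-months post-intervention assessment visit (T4"). Experimental Design puts attrition at about 22%, and adds that the team's earlier rate was nearer 10%.
- **Source of the effect.** CBSM & Physiological Adaptation describes the work cited as reference 124: profiling was done "at baseline and 6- and 12-months post-CBSM in 79 BC survivors randomized to CBSM or health promotion".
- **Comparison in this trial.** Genomic Level specifies "Linear Mixed Models that compare CBSM and C-CBSM groups". Randomization Protocol explains that the comparator was chosen because it delivers the active components of CBSM without the cultural context.
- **Decision rule for genes.** Genomic Level calls a gene differentially expressed if it shows at least a 1.5-fold group difference and "a transcript-level false discovery rate of < 5" percent.
- **Meaning of the 1% level.** To Test Exploratory Hypotheses and Power Analyses present it as the allowance for testing several post-baseline time points within one outcome.

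**The concern.** The sentence makes an unconditional claim of adequacy. That claim needs a sample the trial can deliver and an effect that applies to the contrast being tested. The sample of 100 C-CBSM men at T4 equals the whole arm as enrolled, so it conflicts with both retention figures in the plan. The 1 SD effect is for CBSM against a comparator that was not CBSM, in women with a different cancer. It does not estimate what cultural adaptation adds to CBSM, and the documents give no estimate of that increment on gene expression.

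What is at stake is how Aim 3 will be read, and also Hypothesis 4c, where gene expression is the proposed mediator. If the plan says power was sufficient, a null result invites the conclusion that adaptation has no biological effect. The design may simply have been unable to detect a modest increment.

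**Working it through.** **Inputs.** From the plan: 100 men in C-CBSM at T4, 80% power, two-sided alpha 0.01, a cited effect of 1 SD, 200 enrolled, 140 at T4, and attrition of about 22%. Equal allocation is assumed. The calculation treats men as independent. Delivery in groups of 4 to 8 and any missing blood samples would raise the detectable effects below.

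**1. Reproduce the plan's figure.** For two equal arms, detectable effect = (z₀.₉₉₅ + z₀.₈₀) × √(2/n), with z-sum 2.576 + 0.842 = 3.417 (unrounded inputs).

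- Two arms of 100: 3.417 × √(2/100) = 0.483. This matches 0.48; the noncentral t gives 0.487.
- One sample of 100: 3.417/√100 = 0.342. This does not match.

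So 0.48 is a two-arm calculation with 100 men in each arm at T4, that is, all 200 retained.

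**2. Put in the plan's own retention.** 140/2 = 70 per arm. 200 × (1 − 0.22) = 156, and 156/2 = 78 per arm.

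- 70 per arm: 3.417 × √(2/70) = 0.578 (t: 0.585).
- 78 per arm: 3.417 × √(2/78) = 0.547 (t: 0.553).

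**3. Power for the stated 0.48 SD.** Power ≈ Φ(d√(n/2) − 2.576).

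- 70 per arm: Φ(0.48 × 5.916 − 2.576) = Φ(0.264) = 60% (t: 59%).
- 78 per arm: Φ(0.48 × 6.245 − 2.576) = Φ(0.422) = 66% (t: 65%).

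**4. Power for the cited 1 SD.** At 70 per arm, Φ(5.916 − 2.576) = Φ(3.340) = 99.96% (t: 99.95%). The smaller sample alone does not overturn the conclusion if 1 SD is the right effect.

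**5. Power if the increment over CBSM is smaller.** The documents give no value, so these are assumed effects (noncentral t, two-sided 1%):

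| Assumed increment (SD) | 70 per arm | 78 per arm |
|---|---|---|
| 0.25 | 13% | 15% |
| 0.40 | 41% | 46% |
| 0.50 | 64% | 70% |
| 0.75 | 96% | 98% |
| 1.00 | >99.9% | >99.9% |

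**6. Compare the test level with the gene rule.** Three post-baseline time points under Bonferroni need 0.05/3 = 0.0167, so 1% covers them with room to spare. It makes no allowance for testing many transcripts. The per-transcript p-value implied by a 5% false discovery rate depends on the data. If it were 0.001 to 0.0001 (an assumption), the detectable effect at 70 per arm would be about 0.71 to 0.82 SD (noncentral t). The 1.5-fold condition cannot be put in SD units, because the plan gives no transcript-level SD.

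**The case against.** The strongest reply is that the power claim concerns the effect the plan expects, 1 SD, and that this effect remains detectable. That is correct at 70 per arm and the 1% level, and it largely survives the assumed transcript thresholds too: power for 1 SD at p = 0.0001 is about 97%. A reader might infer that Aim 3 is shown to be underpowered. The documents do not support that, because insufficiency appears only with an assumed smaller increment.

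Three other replies stand in part:

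- **The 1% level is not simply wrong.** It is the plan's declared allowance for time points and could suit a single summary or pathway outcome. The mismatch is with transcript-level discovery only.
- **Gene expression is not shown to be limited to men who give venous blood.** Monocyte isolation needs an in-person draw, but Genomic Level also describes extracting RNA from dried blood spots sent in remotely. A reader might cut the sample sharply for remote collection; the plan gives no such figure and does not say those men are lost to this analysis. Some samples will be missing, since blood draws may be refused or not obtained, but the number is not stated.
- **Aim 3 is already labelled exploratory**, so the primary test is untouched.

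None of this rescues the sample of 100 at T4, or makes an effect against health promotion an estimate of the effect against active CBSM.

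**Conclusion.** The point holds in two parts. First, the stated detectable effect of 0.48 SD is inconsistent with the plan's own retention. The formula was applied correctly; the fault is in the sample size. With 70 to 78 men per arm the detectable effect is about 0.58 to 0.55 SD, and power for 0.48 SD is about 59% to 65% rather than 80%. This rests only on equal allocation and the plan's figures.

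Second, the conclusion of sufficient power is unsupported, because the only effect offered for it belongs to another contrast in another population. This is weaker than saying power is insufficient: at the 1% level, power falls below 80% only if the true C-CBSM increment is under about 0.55 to 0.58 SD, and the documents do not say whether it is. The figures of 13%, 41% and 64% at 70 per arm depend on assumed increments of 0.25, 0.40 and 0.50 SD. The consequence is confined to how exploratory results are interpreted.

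**What to change.** In Power Analyses:

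1. Replace the T4 sample of 100 with the number expected at T4. Reconcile 140 retained with about 22% attrition, or show both: about 0.58 SD at 70 per arm and 0.55 SD at 78 per arm, for 80% power at two-sided 1%. State that the detectable effect is larger if blood samples are missing.
2. Remove the 1 SD effect as support for an active-versus-active comparison. Replace the sufficiency sentence with the detectable effect, saying that no estimate of the increment over CBSM is available.
3. State that the 1% figure applies to a single summary outcome, with allowance for time points, and not to transcript discovery under the false discovery rate and 1.5-fold rule in Genomic Level.

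The change is to wording only; no procedure or sample size need alter. The cost is that a stated figure becomes less favourable and a reassurance about Aim 3 is withdrawn.
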